3.3. Discussion of Subject Population

Inclusion and exclusion were selected to include a homogeneous CLL and WM population treated with BTK inhibitors. Special consideration was taken to avoid disease heterogeneity in order to obtain valid results and this is why only patients who have been on a first-line BTK inhibitor for at least 3 months will be included.

The age limit was set at 50 years old as per the vaccine label.

Exclusion criteria were the result of contra-indications to the vaccine or to the inability to correctly undergo all steps in the research process. In our population, a considerable number of patients also received concomitant rituximab for a period of 6 months (weekly for 1 month and monthly until month 6) at treatment initiation in the context of a clinical trial. We decided not to exclude these patients, but to restrict their enrollment to those who have not had rituximab in the last 12 months. The 12-month time limit was set to minimize the prolonged side effects of rituximab on immunity, but to maximize the inclusion of patients. Data published by Anolik et al in 2006 showed that, although incomplete, B cell recovery occurred by 12 months.²⁹ Even though retrospective data shows that 38.9% of patients with non-Hodgkin's lymphoma develop new-onset hypogammaglobulinemia at a median of 1.4 years post-treatment with a median of 7 doses of rituximab³⁰ and multiple case reports of prolonged hypogammaglobulinemia, happened in the context of rheumatologic diseases or concomitant chemotherapy,³¹⁻³³ this data does not represent our population and thus cannot be applied to them. Currently, no such data exists for this population.

Exclusion of subjects with absolute lymphocyte counts greater than 20,000 cells/ μ L was decided empirically to avoid interference with the assays. An excessive number of lymphocytes could potentially interfere with the laboratory analyses.

4. SUBJECT IDENTIFICATION, RECRUITMENT AND CONSENT

4.1. Method of Subject Identification and Recruitment

CLL and WM subjects on BTK inhibitors will be primarily identified through the Strong Memorial Hospital pharmacy. Lymphoma physicians in the cancer center, all actively involved in research, will be made aware of the study. Subjects may be contacted by their regular team of providers or their regular visits will be used to expose the study by their lymphoma specialist. If patients express interest, a member of the research team will screen the patient, present the study in greater detail and have the patient consent.

Subsequent to consent, a chart review will be performed and captured data will be stored in a secure REDCap database. Privacy is maintained by institutional procedures, which require formal review by appropriate committees prior to any written or telephone correspondence with patients or families.

4.2. Process of Consent

Written consent will be obtained from each subject. Informed consent will be conducted by members of the clinical research team using an IRB-approved informed consent document. The study procedures, their timing, the time and effort asked from the participant, the immediate benefits and the risks associated with the study will be reviewed thoroughly in plain and simple language. The investigator will ensure that written informed consent is obtained from each subject by obtaining the signature and date on the informed consent document prior to the performance of protocol evaluations or procedures. If the informed consent is updated during the study, re-consent will be required from the participants.

If need be, additional time will be allowed to potential subjects to review the document to ensure adequate consent. It will be possible for them to leave with the consent form and review it whenever they feel is most appropriate.

Consent documents will be stored in a secure location at the cancer center as per regular procedures.

A translator and/or translated version of the protocol will be provided as needed.

All subjects will be notified of the delayed one-year blood draw and their permission requested to collect the blood sample and chart review at 24 months.

5. METHODS AND STUDY PROCEDURES

Screening procedures will take place after subjects have consented to study participation.

Subjects will be asked to return to the clinic at a later date to have the baseline blood tests performed and the vaccine administered. We will determine a selection of dates where a certain number of patients will be able to have both procedures performed on the same day.

Blood may also be drawn for baseline testing at the Cancer Center and subjects subsequently administered the vaccine at the outpatient pharmacy on screening day.

After consent, a brief chart and CLL database review will be performed to collect certain variables such as those listed below:

- Age
- Stage at diagnosis
- Date of diagnosis
- 17p deletion (yes/no)
- TP53 mutation (yes/no)
- Mutated status of IVHG (yes/no)
- 11q del (yes/no)
- Presence of trisomy 12 (yes/no)
- Del 13q (yes/no)
- Watch and wait period duration
- Date of BTK inhibitor therapy initiation
- History of zoster reactivation

- History of zoster vaccination
- Immunoglobulin levels before study start
- Use of rituximab in the past (yes/no)
 - Number of cycles
 - Date of last cycle

Prior to the first dose of the vaccine, blood will be collected to assess immunity via measurement of anti-gE and cellular-mediated immunity. Samples will be processed in the cancer center research laboratory. Peripheral blood mononuclear cells (PBMC) will be processed and cryopreserved for future cellular assays and serum will be banked for analysis of anti-gE.

At visit 2, four weeks post-first dose, subjects will be contacted by phone call to report any adverse events. A chart review for severe adverse events will also be performed.

As per the label of the vaccine, the second dose of the vaccine will be administered two months after the first one, at visit 3. One month subsequent to that second dose, at visit 4, a second blood draw will be performed to evaluate the subject's immunogenic response. The initial analyses will be repeated, and response will be measured using statistical methods described below. Safety will be assessed again in the same way as after the first dose. A chart review will be performed to assess CLL/WM progression on BTK inhibitor therapy as determined by subjects' regular team of providers during their latest visit.

These analyses will be repeated 24 months after the last dose of the vaccine to assess long term immunogenicity, at visit 5. A last chart review also be performed to assess incidence of zoster reactivation and disease progression as determined by their team of providers during the latest visit.

Table 1. Schedule of Study Procedures

Visit	Screen*	1*	2	3	4	5
		Dose 1	Safety assessment	Dose 2	Blood draw	Optional Blood draw
Visit window		0	Week 4 ± 1 week	Weeks 8-12	4 Weeks ± 1 week after Dose 2	24 months ± 3 months of Dose 2
Obtain informed consent	X					
Confirm eligibility	X					
Enroll	X					
Vaccine administration	X*	X*		X		
Lab work (anti-gE and CMI)	X*	X*			X	X
Safety assessment (patient-reported AEs)			X		X	

and chart review)						
-------------------	--	--	--	--	--	--

*Note: Administration of the first dose of the vaccine and completion of the lab assays will take place once, either at the screening visit OR at the first visit. If this is done at screening, then screening and visit one will happen within the same visit.

Subjects will be contacted through phone call OR in person at the clinic on for safety assessment.

5.1. Treatment Dosage and Administration

Vaccines will be acquired, stored and administered by the outpatient pharmacy as per the label and with respect to standard-of-care procedures.

Subjects will have a one-vial dose of the vaccine administered by staff from the outpatient pharmacy at that location, and surveillance for immediate adverse effects will be done according to regular procedures.

Cold compresses may be applied to the vaccinated area as needed.

Table 2. Study Drug

Agent	Pre-medications; Precautions	Dose	Route	Schedule
Shingrix vaccine	none.	0.5 µg	IM push	Months 0 and 2

5.2. Efficacy Assessments

Vaccine response, as determined by blood antibody levels to the varicella virus glycoprotein E subunit (anti-gE), will be measured by ELISA. This humoral response will be assessed four weeks after vaccination is complete. In patients who were seropositive before the study, a positive response will be defined as at least a four-fold increase in geometric mean concentration (GMC) of anti-VZV gE antibody as measured per ELISA. Humoral response in seronegative patients at baseline will be defined as at least a four-fold increase from the lower detection limit of the anti-gE antibody assay.

Secondary efficacy objectives include:

1. Measure humoral response at 24 months post-vaccination, which is defined as persistence of anti-gE antibody above test threshold at 24 months.
2. Measure cell-mediated response to vaccination at one month and 24 months after vaccination.
3. Evaluation of CLL/WM progression on BTK inhibitor as determined by treating oncologist at latest assessment, and correlation between progression on BTK inhibitor and vaccine response at 4 weeks and at 24 months post-second dose.

Cellular-mediated response will be determined by measuring PBMC activation (by ELISPOT or flow cytometry) following stimulation with varicella glycoprotein E peptide. PBMC activation at 4 weeks and 24 months post dose will be compared to pre-vaccination activation levels.

a. Safety Assessments

Subjects will be educated to recognize immediate adverse reactions to the vaccine. Patient-reported signs of allergic or hypersensitivity reactions will be assessed and managed by the study team as needed. Only severe adverse effects will be captured in this study. Subjects will be contacted 4 weeks \pm 1 week after each dose of the vaccine for assessment and their chart will be reviewed at the same moment. Severe adverse effects are defined as any grades 3-5 adverse effects included in the CTCAE v5.0 classification.

The decision was made not to report all side effects because the safety of this vaccine has already been proven in large clinical trials, both in a general population of older adults and in immunocompromised patients, including lymphoma patients receiving chemotherapy. These thousands of patients did not experience significant toxicity from herpes zoster vaccination.^{3,13} Moreover, clinically relevant concerns to vaccine administration are grade 3-5 toxicities, which will be captured in the study, both via patient-reported toxicity and through chart review.

b. Assessment of Subject Compliance

All study procedures (vaccine administration and blood draws) will be performed at Strong Memorial Hospital, which will ensure compliance.

c. Costs to the Subject

Cost and administration of the vaccine and all required laboratory testing is covered by the study. Collection and maintenance of research records, laboratory assays and storage of blood samples will also be covered by the study. There will be no direct cost to the subjects to be part of the research project.

d. Payment for Participation

Subjects will not receive payments for their participation in the study.

e. Return of Individual Research Results

Patients will not directly be notified of the results as there will be no direct clinical implications to the observed immunological response. However, that information will be made available through their hematologist after the study is finished.

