Reassessment of serological response was originally planned at one year to evaluate the rate of persistent response. This time point was previously chosen in the general population, and subjects were found to have persistent immunity.³ It was also assessed in a recent phase III trial evaluating response to another inactivated herpes zoster vaccine in immunocompromised patients undergoing autologous stem cell transplant. They were also found to have persistent response.¹³ Due to the COVID-19 pandemic and closure of research laboratories the one year sample could not be collected. The sample will instead be collected at 24 months \pm 3 months. A recent study demonstrated persistent response to the Shingrix vaccine in healthy adults up to 10

years after the initial dose³⁴, suggesting that the 24-month collection is a reasonable time point for reassessment.

This study is designed to obtain valid and comparable results to measure response to a vaccine in a vulnerable population in a fast and uncomplicated way.

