3. CHARACTERISTICS OF THE RESEARCH POPULATION

3.1. Subject Characteristics

a) Number of Subjects:

Target accrual is 30 evaluable CLL or WM subjects receiving treatment with BTK inhibitors. Assuming a 10% drop out rate, we aim to enroll a total of 33 subjects. Participants will be replaced in case of drop out or failure to receive the second dose of the vaccine. Failure to have blood drawn for baseline and/or 4 weeks after vaccination will also warrant replacement.

Subjects will not be replaced if they fail to present to the blood draw 24 months post-vaccination.

In the case of a change of therapy between the first and second dose of the vaccine (including the addition of rituximab), patients will remain on study and will not be replaced. Their data will be included in the estimates of vaccine response in the intent-to-treat analysis but excluded from sub-group analyses.

Based on data from the University of Rochester Cancer Center pharmacy, as of May 2018, 150 CLL and WM patients are on BTK inhibitor therapy and there are approximately 20 new cases per month. A local CLL database confirms those numbers and shows that a total of about 50 patients are on single-agent, first-line ibrutinib as of January 2018. No patient was identified while collecting this data, with respect to patients' confidentiality.

Patients who have started BTK inhibitors come to clinic about every 3 months for routine visits. Based on those numbers, we expect the recruitment of 33 patients to be feasible within 6 months.

b) Gender and Age of Subjects:

Subjects must be at least 50 years old to participate. Patients under 50 years old are excluded as per the label of the vaccine. It is anticipated that most subjects will be in their sixth or seventh decade given the age distribution of CLL²³ and WM.²⁴ There is no upper age limit if the patient meets the other inclusion criteria.

We expect that only a minority of subjects will be diagnosed with WM as compared to CLL because it is a much rarer disease, with only 1400 new cases diagnosed each year in the United States.^{25,26}

All genders are accepted. It is expected that there will be slightly more males than females included in the study as the male-to-female ratio in CLL is normally 1.3-1.7.²⁷ and about 60% of WM patients are males.²⁴

c) Racial and Ethnic Origin:

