3.2. Inclusion and Exclusion Criteria

a) Inclusion Criteria:

Patients will be eligible if:

- They are at least 50 years of age;
- Have been diagnosed with chronic lymphocytic leukemia (CLL) OR Waldenström macroglobulinemia (WM);
- Have been on first-line BTK inhibitor (i.e. ibrutinib or acalabrutinib) for at least 3 months;
- Prior treatment with single agent rituximab is permitted if the last dose was administered more than one year ago;
- Have at least a one-year life expectancy;
- Have a history of varicella (chicken-pox) OR lived in the US or any endemic country for > 30 years'
- Prior radiation therapy is allowed

b) Exclusion Criteria:

Patients will be excluded from the study if they:

- Have a known hypersensitivity to a vaccine component;
- Have had herpes zoster reactivation within the past year;
- Received or were scheduled to receive a live virus vaccine in the period from 4 weeks prior to Dose 1 through 28 days post-second dose;
- Received or were scheduled to receive an inactivated vaccine in the period ranging from 7 days prior to Dose 1 through 7 days post-second dose;
- Are unable to give informed consent;
- Have an absolute lymphocyte count greater than $20,000 \times 10^9/L$;
- Are receiving treatment for CLL or WM with an additional agent other than a BTK inhibitor;

- Had rituximab treatment less than one year prior to study start;
- Had prior chemotherapy.

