13.2. Planned Statistical Analysis

13.2.a Primary Analysis

The estimates of geometric mean antibody titers pre- and post-vaccination, mean fold-changes, and vaccine response rates will be described with 90% (two-sided) confidence intervals. These estimates will be important for designing a future vaccine trial in patients treated with BTK inhibitors with emergence of shingles as the primary outcome. Self-reported and chart-reviewed serious adverse events will be summarized in tabular format by type and grade.

13.2.b Secondary and Exploratory Analyses

As secondary analyses, the change in antibody titers pre and post-vaccination will be evaluated with the Wilcoxon Rank Signed Test for paired data. This test will provide some indication whether the within subject change in titer is statistically different from zero. The change in seroprotection rates pre and post vaccination will be assessed by the exact McNemar test for paired proportions.

As exploratory analyses, the association between baseline characteristics and the achievement of immunological response and change in antibody titers will be assessed using exact non-parametric statistical tests, such as exact Chi-Square test, Wilcoxon Rank Sum test, or Spearman rank correlation tests, depending on the scale of the variables involved. Baseline characteristics of particular interest have been described above and include age, stage at diagnosis, time since diagnosis, presence of high-risk or low-risk features, time since BTK inhibitor therapy initiation, history of zoster reactivation, IgG levels at study entry and use of rituximab therapy. These results will be reported along with descriptive statistics for the purpose of hypothesis generation in future trials.

The disease progression to BTK inhibitor at visit 4 and visit 5 will be determined from the closest assessment by treating oncologist. The association between vaccine response and disease progression at each time point will be assessed with Fisher's exact test.

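### The 24-month humoral response is defined as anti-gE above an unstated threshold, with no baseline reference, so antibody present before vaccination can count as vaccine response

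*Combined protocol and SAP*

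**What the plan says.** Section 5.2 contains two rules for humoral response.

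- **Week 4 (primary).** The rule refers to baseline: "In patients who were seropositive before the study, a positive response will be defined as at least a four-fold increase". Patients seronegative at baseline must reach at least four times the assay's lower detection limit.
- **24 months (secondary).** The objective reads "Measure humoral response at 24 months post-vaccination, which is defined as persistence of anti-gE antibody above test threshold at 24 months". The threshold has no value and is not tied to the detection limit or to a seropositivity cut-off.

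Other sections that bear on the 24-month endpoint:

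- Section 2.2 gives the purpose of the late sample: "Reassessment of serological response was originally planned at one year to evaluate the rate of persistent response". The sample has since moved to 24 months. No denominator is given.
- Section 3.1 says "Subjects will not be replaced if they fail to present to the blood draw 24 months post-vaccination", and Table 1 in section 5 labels visit 5 "Optional Blood draw".
- Section 3.2 makes prior exposure to the virus an entry condition: "Have a history of varicella (chicken-pox) OR lived in the US or any endemic country for > 30 years". Earlier zoster vaccination is recorded under section 5 but is not an exclusion.
- The third secondary objective in 5.2 calls for "correlation between progression on BTK inhibitor and vaccine response at 4 weeks and at 24 months post-second dose". Section 13.2.b plans Fisher's exact test for "The association between vaccine response and disease progression at each time point". Neither names the 24-month response variable.

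**The concern.** The week-4 rule protects against pre-existing antibody by requiring a rise. The 24-month rule drops that protection in a population selected for past exposure, some of whom section 5.2 itself expects to be seropositive at entry.

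Three things follow if the rule is applied as written and the threshold is the seropositivity cut-off:

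- The 24-month rate mixes antibody that was there before vaccination with antibody the vaccine induced.
- It is not comparable with the week-4 rate and can exceed it without any durable vaccine effect.
- If the same variable enters the 24-month Fisher test, patients are classified partly by their serostatus at entry, and the association with progression loses its meaning.

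Section 13.2.a says the response estimates are meant to inform the design of a later trial with shingles as its outcome. A durability rate inflated in this way would be a poor input to that design.

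**Working it through.** **The plan's own figures.** The documents give no figure for the 24-month endpoint. The nearest is Table 3 in section 13.1 (exact two-sided 90% Clopper-Pearson intervals). All 21 intervals reproduce after rounding; for example, 85% at n = 20 gives 65.6–95.8% (table: 66–96%), and 45% at n = 30 gives 29.3–61.4% (table: 29–61%). The same method is used below.

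**Inputs.**

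- r, week-4 response rate: taken from the Table 3 range, 25% to 85%.
- s, share seropositive at baseline: not in the documents; assumed 50% to 100%.
- k, probability that antibody present earlier is still above threshold at 24 months: not in the documents; assumed 80% or 90%.
- Number of 24-month samples: not in the documents; 20 assumed for illustration.

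**Assumptions.** The threshold is the seropositivity cut-off. r is the same in seropositive and seronegative patients. k is the same for pre-existing and vaccine-induced antibody. No seronegative week-4 non-responder is above threshold later, and there are no late four-fold rises.

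**Formulas.**

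- Threshold rule: T = k[s + (1 − s)r]
- Fold-rise rule, upper limit: F = kr
- Share of 24-month threshold responders who were week-4 non-responders: s(1 − r) / [s + (1 − s)r], in which k cancels

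**Results.**

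| s | k | r | T | F (at most) | Share who were week-4 non-responders |
|---|---|---|---|---|---|
| 0.90 | 0.90 | 0.45 | 0.90 × 0.945 = 0.851 | 0.405 | 0.495/0.945 = 0.524 |
| 0.50 | 0.80 | 0.25 | 0.80 × 0.625 = 0.500 | 0.200 | 0.375/0.625 = 0.600 |
| 0.50 | 0.80 | 0.85 | 0.80 × 0.925 = 0.740 | 0.680 | 0.075/0.925 = 0.081 |

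In the first two rows T exceeds the week-4 rate itself (85% against 45%, and 50% against 25%). In the third it does not (74% against 85%).

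With 20 samples, the first row is about 17/20 (90% CI 65.6–95.8%) under the threshold rule, against at most about 8/20 (21.7–60.6%) under the fold-rise rule. Over s = 50–100% and r = 25–85%, the share runs from 0.081 (s = 0.5, r = 0.85) to 0.750 (s = 1, r = 0.25).

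**Sensitivity to unequal retention.** Suppose week-4 responders all stay above threshold and only 70% of seropositive non-responders do. The share becomes 0.7 × 0.495 / (0.45 + 0.7 × 0.495) = 0.435 for s = 0.9, r = 0.45, and 0.7 × 0.375 / (0.25 + 0.7 × 0.375) = 0.512 for s = 0.5, r = 0.25.

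**Limiting case.** With no vaccine effect (r = 0) and full retention (k = 1), T = s. With 30 samples the apparent 24-month response would be 15/30 (90% CI 34–66%) at s = 50% and 27/30 (76–97%) at s = 90%. A fold-rise rule would count about none.

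**The case against.** The strongest reply is that persistence already means persistence of a response achieved earlier, and that staying above an assay threshold at two years is a different but legitimate question from a four-fold rise at week 4. That may well be the intent, and section 2.2 points the same way. But no section states the denominator, so two analysts could report different rates from the same data.

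Section 5 says the visit 4 analyses are repeated at 24 months, which could be read as carrying the four-fold rule forward. Section 5.2, however, gives a separate and explicit 24-month definition, which takes precedence; at best the two conflict.

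Section 13.2.b also has two analyses that refer to baseline. The exact McNemar test compares seroprotection before and after vaccination, but neither seroprotection nor the post-vaccination visit is defined. The linear mixed model describes anti-gE at baseline, week 4 and 24 months, and does give a baseline-referenced view of titres. It supplies neither a response rate nor a binary variable for the Fisher test.

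Some points do stand:

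- A week-4 non-responder may have had a two- or three-fold boost, so the share in the table is not the share with natural antibody only.
- The magnitude depends on assumed seropositivity, and section 1.2 describes hypogammaglobulinemia in CLL, so s could be lower. At s = 20% the share is 0.11/0.56 = 0.20 for r = 45% and 0.03/0.88 = 0.03 for r = 85%.
- That the threshold rule feeds the Fisher test is an inference: it is the only 24-month definition of humoral response, but the test does not name it.

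**Conclusion.** The concern holds. As written, the 24-month rule can count a baseline-seropositive week-4 non-responder as a 24-month vaccine responder. That follows from the text, provided the unstated threshold is at or near the seropositivity cut-off.

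The size cannot be fixed from the documents. Under the stated assumptions the two rules differ by about 45 percentage points in the first case (85% against at most 41%), 30 points in the second (50% against 20%) and 6 points in the third (74% against 68%). The distortion is therefore largest when seropositivity is high and vaccine response low, and small when response is high.

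This is a secondary endpoint on an optional sample in a single-arm pilot. It should be fixed, but it does not threaten the trial's main conclusion.

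**What to change.** In section 5.2:

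- Define 24-month humoral response by the week-4 criterion applied to each patient: at least four-fold over the patient's own baseline, or at least four-fold over the detection limit if seronegative at baseline.
- Report it (a) in all patients with a 24-month sample and (b) among week-4 responders, as persistence.
- State the value of the test threshold. Keep the proportion above it as a description, shown beside the baseline proportion and by baseline serostatus.

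In section 13.2.b, name the fold-rise variable as the one used in the 24-month Fisher test.

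The cost is wording in these two sections, with samples and assays already planned. Section 2.2 shows the study was already under way when the late sample was moved, so the change should be a dated amendment, preferably made before the 24-month results are examined. The reported 24-month rate will probably be lower, and a sustained rise of less than four-fold will count as non-response. The threshold proportion and the mixed model will still show such patients.
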